#### Aim 1: Sample Size Recalculation (November 29, 2017)

The original sample size calculation was performed based on surgical complication rates ( $\leq 12$ months) from Park-Reeves Syringomyelia Research Consortium (PRSRC) estimates (17.8% in PFDD and 2.7% in PFD cases). We originally did not have an estimate for the ICC. Based on the literature, we assumed ICC of 0.05 in our calculations [43]. The overall sample size of enrolled patients would be 238 patients, approximately 119 patients per procedure over the two years of enrollment.

In preparation for our PFD trial annual meeting on November 29, 2017, we performed a sample size re-calculation, using the ICC observed from the 47 patients enrolled in the study and for which complete data was available as of November 28, 2017. It should be noted that the data was only used to calculate the ICC; no interim analyses were performed. The ICC based on the first enrolled 47 patients was 0.000059, much smaller than what was assumed (0.05) for the original sample size calculation. However, we expect this ICC estimate to change with more enrollments.

Enrollment in the trial has increased over time and continues to do so (for example, 10 patients were enrolled in both November and December, 2017 and the total trial enrollment is now 83). However, when calculated at the time of the annual meeting at the end of November 2017, the PCORI CER-1503-29700

Version 6 March 01, 2021

average accrual rate, calculated over the entire 19-month period of the study, was 6 patients per month. Thus, using the conservative projection of 6 patients per month over the course of an enrollment extension ending 12/1/2018, we expect the total number of subjects to be at least 145 (73 + 12 x 6). (73 was the total enrollment when these calculations were made at the end of November; however, as noted above, 10 patients were recruited in December.)

Based on the enrolled 47 patients in the database with complete data as of 11/28/17, the average cluster size is 2.9. If we assume each center enrolls 3 more patients over the enrollment extension, the average cluster size increases to 5.9. With the current ICC estimate of <0.01 and using the original estimates for the complication rates (17.8% in PFDD and 2.7% in PFD), with the projected sample size of 145, we can still reach 84% power by enrolling patients from 24 centers with an average cluster size of 6. The same power level can also be achieved by enrolling patients from 30 centers with an average cluster size of 5.

It should be noted that it is assumed that the average cluster size is 6 in all centers for these calculations. The design effect (DE) concept is used in cluster randomized trials to inflate the sample size of the study, compared to the traditional randomized trials [44]. When cluster size is fixed,  $DE = 1 + (m - 1) \times ICC$ ; where m is the average cluster size and ICC is the intraclass correlation coefficient. In other words, the sample size of the study can be calculated by traditional methods, and should be multiplied by the DE. Under the assumption that m = 6 and ICC = 0.01, DE becomes 1.05. To compare 17.8% vs 2.7% surgical complication rates for a (*not clustered*) randomized trial, with 84% power, and 0.05 type I error rate, we would need to enroll 136 patients total. This is also listed in the sample size calculator above under the "unadjusted box". For a DE value of 1.05, this sample size should be multiplied by 1.05 to find the sample size of a cluster randomized trial to reach same power. Therefore, the sample size of the clustered randomized trial would be 136 x 1.05 = 142.8 ~143.

The variable cluster size is common in cluster randomized trials. Eldridge et al considered the effect of variable cluster size on the sample size calculation for cluster randomized trials [45]. They showed that the DE value can be calculated for variable class sizes. DE' =  $1 + {(cv^2+1) m - 1} x$  ICC; where cv is the coefficient of variation of cluster sizes (standard deviation of cluster sizes divided by the mean cluster size). The cv is 1.08 for our study. If we use the current average cluster size of m = 2.9, DE' becomes 1.06. In other words, the sample size of the study should be inflated to 136 x 1.06 = 144.16~145 to reach 84% power. This assures us that our planned sample size of 145 patients will allow us to reach 84% power even if our cluster sizes will not be fixed at 6.

It should be noted that, as of March 6th 2018, only 1 of 100 enrolled patients was lost to followup. However, to account for a potential 2% loss to follow up on the 145 subjects needed (72 per group), we will recruit a minimum of 148 subjects total (74 per group) and up to 238, over the entire trial enrollment period, which is proposed to be extended to December 31, 2018.

#### Aim 1: Power Calculations

For the purpose of sample size estimation, data from in the Park-Reeves Syringomyelia Research Consortium (PRSRC) were analyzed (ambispective enrollment, n=589 subjects with complete data); specifically, surgical complications  $\leq 12$  months were used to calculate the sample size. In

this dataset, surgical complications were noted in 17.8% of PFDD cases and 2.7% of PFD cases. This is consistent with reported values from a recent meta-analysis, where the rates for CSF-related complications for PFDD and PFD were 18.5% and 1.8%, respectively [27], as well data reported in case series [17, 25] and a systematic review [42]. We expect to observe a similar difference in PFDD versus PFD cases in the proposed study. Because of the clustered randomized nature of the trial, the intraclass correlation coefficient (ICC) should be taken into account. The ICC is defined as the proportion of the between cluster (PRSRC center) variation to the total variation. Since the cluster sizes are small (6 per center), and we have a large number of centers available for enrollment (48 total), the effect of ICC on sample size will be small. Thus, using the PRSRC values of 17.8% for PFDD and 2.7% for PFD, and assuming equal number of subjects per group and twosided type I error rate of 0.05, to reach 90% power, 36 centers averaging 6 subjects per center will be required for the trial assuming the ICC is 0.05. To account for 2% dropout rate, we will recruit 48 centers with a cluster size averaging 6 subjects. Therefore, overall sample size of enrolled patients will be 148 patients, approximately 74 patients per procedure over the enrollment period. These numbers are achievable, as our data suggest there is >500 potential study candidates across the 48-center network over two years.

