#### 9.2 Sample Size and Randomization

#### 9.2.1 Treatment Assignment Procedures

This study is designed as a cluster randomized controlled trial (C-RCT) of the two major neurosurgical treatments for CM+SM: posterior fossa decompression with duraplasty (PFDD) and extradural posterior fossa decompression (PFD). This design was chosen with input from site investigators (neurosurgeons) in order to obtain participation from a large number of pediatric neurosurgeons and reduce crossovers and non-participation resulting from physician bias. During extensive discussions with PRSRC investigators and patient partners, there was significant concern for selection bias due to crossovers and selective enrollment if individual patients were randomized, a known problem in surgical trials [33]. Site investigators felt that having their entire practice randomized to one technique would increase surgeon comfort and experience with that approach, thereby decreasing tendencies for biased enrollment. Consequently, individual PRSRC centers will be randomized to perform either PFDD or PFD. In this design, PRSRC centers will be serve as the unit of inference for comparing PFDD and PFD, and the cluster size is expected to be 6 per center. For cluster randomization, a computer-generated randomization sequence will be generated independently by the study statistician. Overall sample size of up to 238 participants will be enrolled. Approximately 50% participants per procedure over the enrollment period.

Potential participants will be identified, screened, and recruited through the clinical practices of 36 participating PRSRC sties in addition to 8 other sites. In this trial, the randomization unit will be the PRSRC center; therefore, the same intervention will be used for all qualifying patients enrolled at each center. If a surgeon in a PRSRC center strongly believes that a patient should undergo a certain procedure (PFDD or PFD), the patient will not be randomized. Effective randomization will occur through the random distribution of patients to centers employing each procedure (PFDD and PFD).

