For the purpose of sample size estimation, data from in the Park-Reeves Syringomyelia Research Consortium (PRSRC) were analyzed (ambispective enrollment, n=589 subjects with complete data); specifically, surgical complications ≤ 12 months were used to calculate the sample size. In this dataset, surgical complications were noted in 17.8% of PFDD cases and 2.7% of PFD cases. This is consistent with reported values from a recent meta-analysis, where the rates for CSF-related complications for PFDD and PFD were 18.5% and 1.8%, respectively [27], as well data reported in case series [17, 25] and a systematic review [42]. We expect to observe a similar difference in PFDD versus PFD cases in the proposed study. Because of the clustered randomized nature of the trial, the intraclass correlation coefficient (ICC) should be taken into account. The ICC is defined as the proportion of the between cluster (PRSRC center) variation to the total variation. Since the cluster sizes are small (6 per PRSRC center), and we have a large number of centers available for enrollment (47 total), the effect of ICC on sample size will be small. Thus, using the PRSRC values of 17.8% for PFDD and 2.7% for PFD, and assuming equal number of subjects per group and twosided type I error rate of 0.05, to reach 90% power, 36 centers averaging 6 subjects per center will be required for the trial assuming the ICC is 0.05. To account for 2% dropout rate, we originally planned to recruit 40 centers with a cluster size averaging 6 subjects with overall sample size of enrolled patients of 240 patients, approximately 120 patients per procedure over the two years of enrollment.

Aim 1: Sample Size Recalculation (November 29, 2017)

The original sample size calculation was performed based on surgical complication rates (≤ 12 months) from Park-Reeves Syringomyelia Research Consortium (PRSRC) estimates (17.8% in PFDD and 2.7% in PFD cases). We originally did not have an estimate for the ICC. Based on the literature, we assumed ICC of 0.05 in our calculations [43]. The overall sample size of enrolled patients would be 240 patients, approximately 120 patients per procedure over the two years of enrollment.

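### The protocol's Aim 1 power paragraph attaches 90% power at ICC 0.05 to 148 patients, who give about 78% on those assumptions; the 148 comes from a separate recalculation at 84% power

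*Protocol*

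**What the plan says.** The paragraph in Protocol section 9.5, Aim 1: Power Calculations, makes three statements in sequence.

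- The requirement: "to reach 90% power, 36 centers averaging 6 subjects per center will be required for the trial assuming the ICC is 0.05".
- The dropout step: "To account for 2% dropout rate, we will recruit 48 centers with a cluster size averaging 6 subjects".
- The conclusion: "Therefore, overall sample size of enrolled patients will be 148 patients, approximately 74 patients per procedure over the enrollment period".

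The subsection just before it, Aim 1: Sample Size Recalculation (November 29, 2017), tells a different story. It describes ICC 0.05 as the original assumption and gives the original size: "The overall sample size of enrolled patients would be 238 patients, approximately 119 patients per procedure over the two years of enrollment". With an ICC of at most 0.01 and a projected 145 patients, it says "we can still reach 84% power by enrolling patients from 24 centers with an average cluster size of 6". It then adds 2% for loss to follow-up: "we will recruit a minimum of 148 subjects total (74 per group) and up to 238, over the entire trial enrollment period".

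The SAP, section 7.2, has a parallel Aim 1 power paragraph with the same 90% and ICC 0.05 inputs. It marks that calculation as past and ends differently: "we originally planned to recruit 40 centers with a cluster size averaging 6 subjects with overall sample size of enrolled patients of 240 patients". The SAP reaches 148 only in its recalculation.

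**The concern.** A requirement of 216 patients, increased for dropout, cannot yield 148. The paragraph is current text of protocol Version 6, written in the future tense and placed after the recalculation, so it reads as the operative power statement for the primary objective. It credits 148 patients with 90% power and with tolerance of an ICC of 0.05.

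What is at stake is how a non-significant Aim 1 result would be read. Someone relying on this paragraph would judge it against 90% power. The actual figure is about 84 to 85% if the ICC is 0.01, and about 78% if it is 0.05. The ICC is not a settled quantity: the estimate came from 47 patients, and both documents say they expect it to change.

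**Working it through.** **Inputs.** From the protocol's Aim 1 power paragraph: complication rates of 17.8% (PFDD) and 2.7% (PFD), two-sided alpha 0.05, equal arms. From the recalculation: design effect DE = 1 + (m − 1) × ICC for clusters of size m.

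**Formula.** Pooled normal approximation without continuity correction, with n = N / (2 × DE) effective patients per arm:

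power = Φ{ [0.151 × √n − 1.96 × √(2 × 0.1025 × 0.8975)] / √(0.178 × 0.822 + 0.027 × 0.973) } = Φ{ (0.151 × √n − 0.841) / 0.415 }

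**Step 1: the original plan.** For 90% power the formula gives 83 per arm, 166 in total. At m = 6 and ICC 0.05, DE = 1.25, so 166 × 1.25 = 207.5 patients, or 34.6 centers of 6. Rounded up to equal whole centers per arm, that is 18 + 18 = 36 centers, or 216 patients. Power at 216 is 91.2%. The 36 centers reproduce.

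**Step 2: the recalculation.** At m = 6 and ICC 0.01, DE = 1.05. With 145 patients, n = 145 / 2.10 = 69.0 and power is 84.1%. The stated 84% reproduces. Then 145 / 0.98 = 147.96, which rounds to 148. This is where 148 comes from.

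**Step 3: the dropout step.** 216 / 0.98 = 220.4, so 221 patients, or 37 centers of 6. The stated 48 × 6 = 288 is 33% above 216.

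**Step 4: 148 on the paragraph's own assumptions.** n = 148 / 2.50 = 59.2. Power = Φ{ (0.151 × 7.694 − 0.841) / 0.415 } = Φ(0.77) = 78.0%.

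| Patients | ICC | m | DE | Power (pooled) |
|---|---|---|---|---|
| 216 | 0.05 | 6 | 1.25 | 91.2% |
| 145 | 0.01 | 6 | 1.05 | 84.1% |
| 148 | 0.01 | 6 | 1.05 | 84.8% |
| 148 | 0.05 | 6 | 1.25 | 78.0% |
| 148 over 48 centers | 0.05 | 3.08 | 1.104 | 82.9% |
| 238 | 0.05 | 6 | 1.25 | 93.6% |

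**Step 5: other formulas.** For 148 patients at ICC 0.05 and m = 6, power is 79.9% unpooled, 83.7% by arcsine and 67.7% with continuity correction. Over 48 centers it is 84.5% unpooled and 87.9% by arcsine. None of these reaches 90%. By the pooled formula, 148 patients give 86.5% even with no clustering at all.

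**Step 6: the surrounding planning figures.**

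- Original total: 238 (protocol recalculation) against 240 (SAP section 7.2). The protocol's power paragraph implies 288.
- Centers in the protocol: 48 in section 4.3 and in the power paragraph. Section 9.2.1 gives "36 participating PRSRC sties in addition to 8 other sites", which is 44.
- Centers in the SAP: 36 + 7 = 43 participating in section 7.2.1. The power paragraph gives 47 available and 40 originally planned.

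These center counts are not all the same quantity, and only the 40 is explicitly labelled as the original plan. No stated total is 216 plus 2%.

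**The case against.** The strongest reply is that this is an unfinished edit to one paragraph. The recalculation immediately before it derives 148 correctly at 84% power, and the later SAP keeps the two calculations apart. A reader of either document in full would find the right figure. That stands, and it limits the consequence. It does not mend a paragraph that states a power its own sample size does not deliver.

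It can also be said that the protocol's size is a range, 148 up to 238, and that 238 patients would give about 94% pooled (89.9% with continuity correction) at ICC 0.05. That is right. The shortfall applies at 148, which is the figure the power paragraph gives and the only size the SAP plans for.

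Three stronger readings are tempting but not supported.

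- A reader might infer that 148 is too few. The documents justify 148 by the recalculation, which reproduces; only its link to 90% and ICC 0.05 is wrong.
- A reader might infer an undeclared 10% allowance behind 238 and 240, since 216 × 1.10 = 237.6 and 216 / 0.90 = 240. No section mentions 10%. A continuity-corrected calculation also arrives at 240 (96 per arm × 2 × 1.25), so the origin cannot be established.
- A reader might doubt the unequal-cluster check because it pairs the interim mean cluster size of 2.9 with a coefficient of variation (cv) of 1.08. On the plan's own projection of 3 more patients per center, the cv becomes 1.08 × 2.9 / 5.9 = 0.53. The requirement is then 136 × 1.0656 = 144.9, which confirms 145.

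**Conclusion.** The power statement is wrong as written. On the paragraph's own assumptions, 148 patients give 78% rather than 90%, a gap of 12 points, or about 7 points if they are spread over 48 centers. On the recalculation's assumptions (ICC 0.01, clusters of 6) they give 84.8%, about 5 points below the stated figure.

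These results assume the plan's complication rates, equal arms, equal clusters and the pooled formula. That formula is the like-for-like choice because it reproduces both the 36 centers and the 84%. The exact shortfall depends on the formula, but its existence does not.

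The 148, the primary endpoint and the analysis are unaffected.

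**What to change.** In the protocol's Aim 1 power paragraph:

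- Label the 90%, ICC 0.05 calculation as the original plan, as the SAP does, and detach it from 148.
- State that 148 rests on the November 2017 recalculation, with about 84 to 85% power (pooled) at ICC 0.01 and clusters of 6.
- Add that power at 148 would be about 78% if the ICC were 0.05, and name the formula used.

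Across both documents:

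- Reconcile the original total (238, 240 or the implied 288) and the 2% allowance said to lie behind it.
- Reconcile the center counts (48, 44, 43, 47 and 40), saying for each whether it means available, participating or originally planned.

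The cost is the wording of one protocol paragraph and the reconciliation of a few planning figures. No patients are added and no outcome data are needed. The downside is a less favourable stated power.

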#### Aim 2: Non-Inferiority Margins and Power

The non-inferiority margins for this trial were determined in conjunction with a panel of experts on CM+SM and related treatment (the Park-Reeves investigators), our non-physician stakeholder partners, and our patient partners, [name], [name], [name], [name], [name], [name], and [name]. Using a clinical, Delphi-type approach [46] for the complex measure of clinical improvement, the research team agreed upon a non-inferiority margin of no more than 20% lower response for PFD from the PFDD group. The clinical improvement rate for the PFDD group was provided as 78.6% in the Durham study [27]. Thus, with the sample size of 72 subjects per group (after an assumed 2% dropout), we concluded non-inferiority of the PFD to PFDD with a margin of 0.17 units ( $\alpha$ =0.05, 80% power). This corresponds to clinical improvement rate of 61.6% in the PFD group. It was shown in the Durham study that the clinical improvement following PFD was 64.6%.

Determine if PFD provides non-inferior clinical improvement compared to PFDD (Non-inferiority Design)							
Outcome	PFDD	PFD	Data Source	Non-inferiority Margin	α-level	Subjects per group	Power
Clinical Improvement	44/56 (78.6%)	51/79 (64.6%)	Durham [27]	0.17	0.05	72	80%

For these calculations, the drop-out rate is assumed to be 2%, and the one-sided type I error rate is 0.05.

After determination with the Delphi method, the non-inferiority margin was subsequently confirmed as appropriate using Rothman's 95-95 approach [47, 48] and the FDA guidelines for selecting the non-inferiority margin for non-inferiority clinical trials [49]. Using these methods, the non-inferiority margin was estimated using the effect of the standard treatment (PFDD) from Durham's meta-analysis [27], with the lower 1-sided 95% confidence interval for the random-effects meta-analysis calculated to be used as a non-inferiority margin. When the data from the PFDD group from the Durham study was used for the clinical improvement outcome, the 95% lower 1-sided confidence interval from the random effects model was calculated as 0.611. In our proposal, we defined the non-inferiority margin as the difference between the rates. For the clinical improvement outcome, this corresponds to the non-inferiority margin of 0.786 - 0.611 = 0.175 PCORI CER-1503-29700

Version 6 March 01, 2021

units. Therefore, our recommended non-inferiority margin of 0.17 units, for the clinical improvement outcome, is smaller than the FDA-recommended largest acceptable non-inferiority margin of 0.175 units.

In contrast to clinical improvement, syrinx regression is an objectively measurable and easily quantifiable outcome. It is measured by comparing syrinx size on MRI scans obtained before and after surgery. When the effective sample size is 68 subjects per group, and assuming 89.1% syrinx regression rate in the PFDD group [27], the non-inferiority margin is 0.135 units to reach 81% power. A non-inferiority margin of 0.135 units represents no more than 13.5% reduction from the PFDD group in terms of syrinx regression. Note that a one-sided type I error rate of 0.05 was assumed, and the 'Two group test of equivalence in proportions' option in nQuery Advisor was used.

Determine if PFD provides non-inferior syrinx regression compared to PFDD (Non-inferiority Design)							
Outcome	PFDD	PFD	Data Source	Non-inferiority Margin	α-level	Subjects per group	Power
Syrinx Regression	261/293 (89.1%)	31/38 (81.2%)	Durham [27] and PRSRC	0.135	0.05	72	81%

For these calculations, the drop-out rate is assumed to be 2%, intra-class correlation coefficient is 0.05, and the one-sided type I error rate is 0.05.

# Aim 3: Power Calculations

Based on preliminary data using the Chiari Health Index in Pediatrics (CHIP)[50], we observed a 0.12±0.16 unit improvement in Quality of Life (QOL) scores following PFDD. Our sample size of 72/group (effective sample size of 68/group) will provide 82% power to detect a 0.20±0.16 unit improvement in CHIP QOL scores following PFD ( $\alpha = 0.05$ ). Both from an analytical standpoint and from the view of PRSRC investigators and our patient partners, this value represents both a significant and meaningful increase in QOL.

# 10. DATA COLLECTION AND QUALITY ASSURANCE

# **10.1 Data Collection Forms**

The DCC will create source documents and disseminate them to all of the participating centers. Ultimately, the data on the source documents will be transcribed to an electronic database created by the DCC. Similarly, imaging will be uploaded to a separate electronic platform, the Central Neuroimaging Database Archive (CNDA). This platform is maintained and managed at Washington University-St. Louis.

# 10.2 Data Management

The DCC will monitor each site's data and interpret the respective imaging. The University of Iowa will oversee the DCC and process data in the following manner:

- Data Management
  - Design and modify data dictionary (the information that is being collected)
  - Design and modify SQL Server database
  - Quality Control
- Retrieval and Reports

- Assist in preparation of data quality reports
- Assist in preparation of progress reports
- Design and Analysis
  - Consult with investigators in design and analysis of research questions

